6.3.2 Criteria for Conditional Withholding of Omecamtiv Mecarbil due to Potential Hepatotoxicity

For subjects who do not meet the criteria for permanent withholding of IP outlined above, omecamtiv mecarbil should be withheld if ANY of the following criteria are met, and the subject should be evaluated for DILI:

- Elevation of either AST or ALT according to the following schedule:

Baseline AST or ALT value	AST or ALT elevation
Any	> 8x ULN at any time
Any	> 5x ULN but < 8x ULN for \geq 2 weeks
Any	> 5x ULN but < 8x ULN and unable to adhere to enhanced monitoring schedule
Any	> 3x ULN with clinical signs or symptoms that are consistent with hepatitis (such as right upper quadrant pain/tenderness, fever, nausea, vomiting, jaundice).

- Or: TBL > 3x ULN at any time
- Or: ALP > 8x ULN at any time

Omecamtiv mecarbil should be withheld pending investigation into alternative causes of DILI. If investigational product(s) is withheld, the subject is to be followed according to recommendations in [Appendix A](#) for possible DILI. Rechallenge may be considered if an

alternative cause for impaired liver tests (ALT, AST, ALP) and/or elevated TBL is discovered, and the laboratory abnormalities resolve to normal or baseline ([Section 6.3.3](#)).

6.3.3 Criteria for Rechallenge of Omecamtiv Mecarbil After Potential Hepatotoxicity

The decision to rechallenge the subject should be discussed and agreed upon unanimously by the subject, investigator, and Amgen.

If signs or symptoms recur with rechallenge, then omecamtiv mecarbil should be permanently discontinued. Subjects who clearly meet the criteria for permanent discontinuation (as described in [Section 6.3.1](#)) should never be rechallenged.

6.4 Concomitant Therapy

Throughout the study, investigators may prescribe any concomitant medications or treatments deemed necessary to provide adequate supportive care except for those listed in [Section 6.6](#). All appropriate concomitant medications taken by a subject while on study are to be recorded.

6.5 Product Complaints

A product complaint is any written, electronic or oral communication that alleges deficiencies related to the identity, quality, durability, reliability, safety, effectiveness, or performance of a drug(s) or device(s) after it is released for distribution to market or clinic by either Amgen or by distributors and partners for whom Amgen manufactures the material. This includes any drug(s) or device(s) provisioned and/or repackaged/modified by Amgen. Drug(s) or device(s) includes investigational product. Any product complaint(s) associated with an investigational product(s) or non-investigational product(s) or device(s) supplied by Amgen are to be reported according to the instructions provided in the IPIM.

6.6 Excluded Treatments, Medical Devices and/or Procedures During Study Period

Other investigational procedures while participating in this study are prohibited. Medications or foods that are known potent inducers or inhibitors of CYP3A4 (see [Section 4.1.2](#) and [Appendix D](#)) are prohibited up to the EOS visit, occurring on week 20.

7. STUDY PROCEDURES

7.1 Schedule of Assessments

Table 2. Schedule of Assessments

Timepoint - Day/Week/Month (window)*	Screen	D1	D7	W2 D15 (-3)	W4 D28 (+3)	D34 (+3)	W8 D56 (±3)	D62 (+3)	W12 D84 (±3)	W16 D112 (±3)	W20 ^a D140(+3) EOS
General Procedures											
Informed consent	X										
Medical history and demographics	X										
Vital Signs (HR, BP)	X	X ^c		X	X		X ^j		X	X ^k	X
AEs/SAEs/PEPs ^b	X	X		X	X		X		X	X	X
AEs/SAEs and IP compliance verification by phone or other contact			X			X		X			
Concomitant therapy	X	X		X	X		X		X	X	X
Physical examination	X										X
Body height		X									
Body weight		X		X			X		X	X	X
ECG	X	X ^c		X	X		X ^d		X	X ^d	X
Echocardiogram	X						X ^j			X ^k	
Central Laboratory											
PK samples ^e		X ^c		X ^c	X ^c		X ^j		X ^c	X ^k	
Chemistry (including eGFR at screening)	X			X			X		X	X	X
Hematology	X			X			X		X	X	X
Urinalysis		X					X				X
Troponin I, CK-MB ^e		X ^c		X	X		X		X	X	X
NT-proBNP		X ^c			X		X			X	
Samples for Development Therapeutic Monitoring Assay					X				X		
Serum pregnancy, FSH/LH or estradiol ^f	X										X
Digoxin sample (in subjects receiving digoxin)		X		X							
Investigational Product^g											
IP dispensation and/or administration at site		X		X	X		X		X	X ^h	
IP diary dispensation or collection ⁱ		X								X	
IP reconciliation (tablet count)				X	X		X		X	X	

Footnotes displayed on the next page of the Table

AE = adverse event; BP = blood pressure; CK-MB = creatine kinase-MB; ECG = electrocardiogram; eGFR = estimated glomerular filtration rate; EOS = end of study; HR = heart rate; IP = investigational product; NT-proBNP = N-terminal pro-B-type natriuretic peptide; NYHA = New York Heart Association; PEP = potential endpoint; PK = pharmacokinetic; SAE = serious adverse event.

Please note: vital signs, ECGs, and laboratory samples can be collected at any time during the study visit, unless otherwise specified below.

Visit Windows: For week 2 visit, the visit date could be 3 days prior to the scheduled date of W2; for week 4 visit, the visit date could be 3 days after the scheduled date of W4; for weeks 8, 12, and 16, the visit dates could be 3 days prior to or after the scheduled date of W8, W12, and W16, respectively; for week 20 visit (EOS), the visit date could be up to 3 days after the scheduled date of W20. The Day 34 and 62 telephone calls could be 3 days after the scheduled date of contact.

^a If early discontinuation, week 20 (EOS) assessments should be performed as close as possible to time of discontinuation

^b Serious adverse events are collected from signing the informed consent until 30 days after the last dose of IP or EOS, whichever is later, adverse events and PEPs from randomization until EOS, recording of PEPs and hospitalization only during visits to the study site (day 1, weeks 2, 4, 8, 12, 16, 20 [EOS]); if subject is not seen at the study site, AEs/SAEs/PEPs can be collected by phone

^c Predose in the morning, at study site

^d Performed as close as possible after the collection of PK sample at 2 hours \pm 30 minutes following IP administration.

^e If cardiac troponin is measured locally to evaluate suspected myocardial ischemia or infarction, send samples for troponin I/CK-MB, and PK (up to 5 days after last dose of IP) to the central laboratory

^f Serum pregnancy testing in females of childbearing potential, FSH/LH or estradiol at screening only, and only if applicable per exclusion criteria.

^g IP is taken twice daily except on the last day of administration (week 16 visit). Subjects randomized to 37.5 mg BID target dose and 50 mg BID target dose will initiate administration at 25 mg BID. Subjects will be up-titrated to 37.5 mg BID or 50 mg BID target dose at the week 4 visit based on steady state $C_{predose}$ result from week 2. Subjects who do not have a week 2 PK value in time for dose adjustment at the week 4 visit, will be up-titrated at week 8 based on steady state $C_{predose}$ result from week 2, if available. Subjects will be up-titrated at the week 4 or week 8 visits only if the week 2 $C_{predose}$ is < 200 ng/mL. Otherwise, they will continue at 25 mg BID.

^h Details of IP dispensation and reconciliation are described in the IPIM; dispensation and reconciliation timepoints may differ from the timepoints shown above; IP not dispensed at week 16 visit.

ⁱ Paper Diary will be dispensed at Day 1 and will be collected at week 16. Subjects will be instructed to enter each administration of IP from Day 1 to week 16 or early termination. The date and time of administration will be noted.

^j Vital signs and PK samples at predose, at 2 hours \pm 30 minutes; 4 hours \pm 30 minutes; 6 hours \pm 30 minutes; 8 hours \pm 30 minutes after IP administration in the morning (0 h = start of IP); echocardiogram performed as close as possible after the collection of PK sample at 2 hours \pm 30 minutes following IP administration.

^k Vital signs and PK samples at predose and at 2 hours \pm 30 mins following IP administration. Echocardiogram should be performed as close as possible after the collection of PK sample at 2 hours \pm 30 minutes following IP administration.

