7.4 Treatment Period

Adverse events, serious adverse events, PEPs, and concomitant medications, will be reported until EOS at week 20. If a subject is not seen at the study site, adverse events/serious adverse events/PEPs should be collected by phone. For details on reporting of adverse events and serious adverse events, please refer to [Section 9](#).

The following procedures will be completed during the study at the times designated in the Schedule of Assessments ([Table 2](#)).

- Vital signs (HR, BP)
- Adverse events/serious adverse events/PEPs, if applicable
- Concomitant therapy
- Body height, at Day 1 visit only
- Body weight, at Day 1, weeks 2, 8, 12, and 16
- ECG (centrally read), at Day 1, weeks 2, 8, 12, and 16
- Echocardiogram, at weeks 8 and 16 (centrally read)
- Blood samples for chemistry and hematology, at weeks 2, 8, 12, and 16
- Blood samples for digoxin levels (only in subjects taking digoxin), at Day 1 and week 2
- PK sample collection, at Day 1, weeks 2, 4, 8, 12, and 16
- Urine sample for urinalysis, at Day 1 and week 8
- Blood samples for troponin I, CK-MB, at Day 1 and weeks 2, 8, 12, and 16
- NT-proBNP, at Day 1, and weeks 4, 8, and 16
- Therapeutic Monitoring Assay sample collection at weeks 4 and 12
- IP dosing on site, at Day 1, weeks 2, 4, 8, 12, and 16
- IP dispensation, at Day 1, week 4 and week 8
- IP reconciliation (tablet count) at weeks 2, 4, 8, 12, and 16
- Diary dispensation, Day 1
- Return diary, week 16

7.4.1 Telephone Contact Days 7, 34, and 62

- AEs/SAEs and IP compliance will be verified by phone or other contact

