10.8.3 Vital Signs

Vital signs, including HR (based on measurement of pulse), and their change from baseline will be summarized by actual treatment group and scheduled assessment.

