Appendix A. Analytical Study Week Assignments

Selected endpoints will be summarized by scheduled study visits in descriptive analyses. Since the actual visits may not exactly coincide with their scheduled visit day, the actual visit day is mapped to the study visit by non-overlapping consecutive intervals covering the entire time continuum. The mapping intervals for all distinct schedules are summarized in the following table, for non-PK endpoints:

Scheduled visit	Actual Visit Day (Study Day)							
	VS*, CC, ECG	WT, CH, HE	PE	NT	ECHO	UR	DG	NYHA
BL/Day 1	≤ 1	≤ 1	≤ 1	≤ 1	≤ 1	≤ 1	≤ 1	≤ 1
Day 15 (Week 2)	> 1 – ≤ 21	> 1 – ≤ 35						> 1
Day 28 (Week 4)	> 21 – ≤ 42			> 1 – ≤ 42				
Day 56 (Week 8)	> 42 – ≤ 70	> 35 – ≤ 70		> 42 – ≤ 84	> 1 – ≤ 84	> 1 – ≤ 98		
Day 84 (Week 12)	> 70 – ≤ 98	> 70 – ≤ 98						
Day 112 (Week 16)	> 98 – ≤ 126	> 98 – ≤ 126		> 84	> 84			
Day 140 (Week 20)	> 126	> 126	> 1			> 98		

VS: vital signs; WT: body weight; CC: cardiac troponin and CK-MB; PE: physical examination; NT: NT-proBNP; ECHO: electrocardiography; CH: chemistry; HE: hematology; UR: urinalysis; DG: Digoxin.
*Vital signs on week 8 and 16 are to be measured multiple times for E-R analysis purpose, and the value before morning dose will be used for non-PKPD analysis.

Handling multiple records assigned to an analytical study day/week:

If there is more than one record in a study week interval, the analytical record for that specific study week will be defined as the record closest to the scheduled study day of that specific study week ($7 \times$ study week + 1). If two records are equidistant from the scheduled day, then the earlier record will be chosen. If there are multiple records on the same day, the last record will be used.

Exceptions to these rules are:

- vital signs, the latest one prior to first IP administration on that day will be used in the non-PKPD analysis;
- cardiac troponin, CK-MB, and creatine kinase, where the worst non-missing value within the interval will be used in the analysis.

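### Vital signs at weeks 2, 4 and 12 have no fixed timing relative to the on-site dose, while Day 1, week 8 and week 16 require a predose set, so by-visit changes from baseline may mix the two

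*Protocol*

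**What the plan says.** The general note under Protocol Table 2 reads "vital signs, ECGs, and laboratory samples can be collected at any time during the study visit, unless otherwise specified below". In the vital-signs row, three on-site dosing visits carry a timing footnote:

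- Day 1, footnote c: "Predose in the morning, at study site".
- Week 8, footnote j: "Vital signs and PK samples at predose, at 2 hours", followed by sets at 4, 6 and 8 hours.
- Week 16, footnote k: "Vital signs and PK samples at predose and at 2 hours".

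Weeks 2, 4 and 12 carry a plain mark. At those three visits footnote c is attached to the PK sample but not to vital signs. Protocol 7.4 lists "IP dosing on site, at Day 1, weeks 2, 4, 8, 12, and 16", so each is a dosing visit. Protocol 7.2.4 covers rest, posture and repeats, but not timing relative to dose.

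On the analysis side, SAP 10.8.3 says that vital signs and "their change from baseline will be summarized by actual treatment group and scheduled assessment". The note to the SAP Appendix A table says that at weeks 8 and 16 "the value before morning dose will be used for non-PKPD analysis". Among the exceptions for handling multiple records, Appendix A adds: "vital signs, the latest one prior to first IP administration on that day will be used in the non-PKPD analysis".

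**The concern.** Change from baseline in vital signs is a safety endpoint, and safety and tolerability form one of the two primary objectives. The summary is read across visits: baseline, then weeks 2, 4, 8, 12 and 16. That reading assumes each visit captures the same point in the dosing interval. Under the current schedule, baseline and weeks 8 and 16 are fixed at predose, and the three visits between them are left open. A change at week 2, 4 or 12 that differs from week 8 could then reflect when the cuff went on as well as time on treatment or dose.

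Week 4 deserves separate mention because it is the main up-titration visit. A blood pressure or heart rate that meets a withholding rule in Protocol 6.2.1.2 can affect the on-site dose only if it is read before that dose.

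**Working it through.** The plan gives no figure to reproduce. The check sets the timing rules side by side and counts visits.

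**Timing by visit**

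| Visit | On-site dose (7.4) | Vital-sign timing (Table 2) | Value in the by-visit summary |
|---|---|---|---|
| Day 1 | yes | predose (c) | predose baseline |
| Week 2 | yes | unrestricted | before or after dose |
| Week 4 | yes | unrestricted | before or after dose |
| Week 8 | yes | predose plus 2, 4, 6, 8 h (j) | predose (SAP Appendix A) |
| Week 12 | yes | unrestricted | before or after dose |
| Week 16 | yes | predose plus 2 h (k) | predose (SAP Appendix A) |

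The SAP 6.2 definition of baseline works by date only. Footnote c is what makes the Day 1 reading predose.

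**Count**

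- On-treatment visits with vital signs: weeks 2, 4, 8, 12, 16 = 5.
- Without a predose requirement: weeks 2, 4, 12 = 3.
- Planned subject-visits: 80 × 5 = 400, of which 80 × 3 = 240 lack the requirement (240/400 = 60%).
- Per arm: 20 × 3 = 60 of 20 × 5 = 100.

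The 240 is a ceiling. Sites that take vital signs on arrival contribute none, so the number actually post-dose lies between 0 and 240.

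**Effect on a visit mean (illustration with assumed quantities)**

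Let f be the share of sets at a visit taken after the dose, and d the average post-dose minus predose shift. The visit mean moves by f × d: by 0 if f = 0, and by d if f = 1. The documents supply neither f nor d, so no shift in mmHg or beats per minute can be stated.

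For two arms at the same visit, blinding gives no reason to expect f to differ. Both arms then share the same mix of timings. The contrast is not biased by timing, although it refers to a blend of predose and post-dose states.

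**The case against.** The strongest reply is that this is harmless flexibility. The extra sets at weeks 8 and 16 exist, by the SAP's own note, for exposure-response analysis. Weeks 2, 4 and 12 need only one set. Subjects arrive undosed for the PK sample, and many sites would probably measure vital signs on arrival. All analyses are descriptive, and the PK endpoints, SET and sample size are untouched. Most of this stands and is why the severity is low. It does not change the fact that a compliant site may measure after dosing.

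Three stronger readings are tempting, and the documents do not support them.

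- **A reader might infer that the SAP would turn a lone post-dose reading into a missing value**, because Appendix A asks for the latest value before dosing. That line is an exception under the heading on multiple records and chooses among several readings. Where only one set exists, the visit-window table assigns it. The missing-value reading is strained.
- **A reader might infer that subjects receive their first higher dose at week 4 without the vital-sign check that week 8 provides.** No text says that the on-site week 4 dose comes from the new supply. Table 2 refers dispensing details to a separate manual and allows dispensing timepoints to differ. Nor are the week 8 predose vital signs presented as a condition for titration, which depends only on the week 2 predose concentration. The 6.2.1.2 rules apply throughout treatment, a contact is scheduled 6 days after the week 4 visit, and the DMC reviews unblinded data about monthly.
- **A reader might take the simulated exposures in Protocol Table 1, or the half-lives in 2.2.2.1, as evidence of a blood-pressure or heart-rate effect.** They describe concentrations and give no BP or HR shift.

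**Conclusion.** The point holds as a question of comparability across visits. Table 2 expressly permits the only scheduled vital-sign set at weeks 2, 4 and 12 to precede or follow the on-site dose, while baseline and the analysed values at weeks 8 and 16 are predose. By-visit change from baseline may therefore mix timings at 3 of 5 on-treatment visits. The extent is unknown: 0 to 240 of 400 planned subject-visits, with no documented shift. The count assumes all 80 planned subjects attend every visit.

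The conclusion that same-visit arm comparisons are not biased assumes that measurement timing is unrelated to arm, which blinding supports.

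A possible secondary benefit of fixing the timing is that BP and HR would be read before the on-site dose at week 4, the main up-titration visit. That may be the first higher dose for up to 2 × 20 = 40 subjects in the titration arms, but the documents do not say so. This is a cheap improvement of low severity, not a defect in the primary analysis.

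**What to change.** In Protocol Table 2, attach footnote c to the vital-sign entries at weeks 2, 4 and 12. The timing then matches Day 1 and the analysed values at weeks 8 and 16, and the week 4 reading precedes the on-site dose.

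Add one sentence to SAP Appendix A: if the only vital-sign set at a dosing visit was taken after the morning dose, the value is kept for that visit, its time relative to dose is recorded, and it is flagged in the summary and listing. It should not be set to missing, since that would discard observed safety data in arms of about 20 subjects.

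The cost is a protocol edit, with the investigator agreement and ethics approval that Protocol 12.1 requires for an amendment, and a fixed order of procedures at three visits. No visit or scheduled measurement is added, because subjects already attend undosed for the predose PK sample. The step is the same in every arm, so it reveals nothing about dose.

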7.2 General Study Procedures

7.2.1 Informed Consent

All subjects or their legally authorized representative must personally sign and date the IRB/IEC approved informed consent before any study specific procedures are performed. See [Section 11.1](#) for further details.

7.2.2 Medical History

The subject's relevant medical and surgical history will be obtained prior to enrollment and recorded in the eCRF.

7.2.3 Concomitant Therapy

Prior therapies that were being taken within 30 days prior to screening through the completion of the study should be reported on the eCRF. The therapy name, indication, dose, frequency, route, and start date and stop date should be recorded in the eCRF.

7.2.4 Vital Signs

The following measurements must be performed: systolic/diastolic BP and HR. Subjects should be in a seated or semi-recumbent position for at least 5 minutes before taking vital sign measurements. The position selected for a subject should be the same that is used throughout the study and documented on the vital sign eCRF. Any abnormal measurements may be repeated and reported on the eCRF. All values must be verifiable on the source documents.

7.2.5 Investigational Product Administration Diary

Subjects will be supplied with a diary during the Day 1 visit in which to record the date and time of each administration of IP taken away from the site. Study site staff will review the diary with the subject at each clinic visit for compliance with IP dosing. The study site staff will make a copy of the diary at each visit and transcribe the date and time of each morning and evening dose of IP taken, as directed by the Electronic Case Report Form Completion and Query Resolution Guide. The diary will be retained at the study site as part of the source documentation once the subject has completed his/her study participation.

7.2.6 Adverse Events

Refer to [Section 9](#) for information on the definitions and reporting procedures for adverse events and serious adverse events.

7.2.7 Potential Endpoints

Deaths, hospitalizations and selected nonfatal cardiovascular events will be reported on an ongoing basis to Amgen or designee, as potential endpoints (PEPs). An independent CEC committee will adjudicate deaths, all hospitalizations, and selected nonfatal CV events (including possible MI or ischemia). The adjudicated events will include, but may not be limited to the following: cardiovascular death, HF, acute myocardial infarction, myocardial ischemia, unstable angina, and resuscitated sudden death. Only events occurring after subject randomization until completion of the study will be adjudicated.

7.2.8 Hospitalizations

Information about all hospitalizations up to the EOS (week 20) will be collected.

7.2.9 Physical Examination

The screening physical examination will be a complete physical examination including height and weight. Breast, genital, and rectal examinations are not required at any study visit unless specific evaluation is warranted in accordance with the standard of care.

Physical examination findings at screening are to be recorded in the medical and surgical eCRF. The physical examination at the EOS visit at week 20 will consist of an examination to monitor for any changes from the screening physical examination. Any clinically significant change from the baseline physical examination, which represents deterioration, is to be recorded on the Events eCRF.

7.2.10 Physical Measurements

Height and weight should be measured without shoes at Day 1. Weight only will be measured at weeks 2, 8, 12, 16, and at week 20 (EOS).

7.2.11 Electrocardiogram

At each scheduled visit where ECGs are being obtained, three 12-lead ECGs will be collected consecutively approximately 30 seconds to 1 minute apart. Using equipment supplied to each site, all protocol-specified ECGs will be acquired and transmitted to the centralized ECG services provider. The principal investigator or designated physician will review acquired ECGs. One (1) signed, original ECG tracing should be retained with the subject's source documents. At the request of the sponsor, the original ECG should be made available to Amgen.

Subject must be in supine position in a rested and calm state for at least 5 minutes before ECG assessment is conducted. If the subject is unable to be in the supine

position, the subject should be in most recumbent position as possible. The ECG must include the following measurements: HR, QRS, QT, QTc, and PR intervals.

The centralized ECG services cardiologists will perform standard interpretations of all tracings. A cardiologist reviewed ECG report will be provided to the study site.

Investigators must initial and date the ECG reports upon receipt. If the investigator's interpretation of any protocol-specified or unscheduled ECG differs from that supplied by centralized ECG services provider, it is the responsibility of the investigator to make the final clinical decisions. The investigator's interpretation does not need to be reconciled with that supplied by centralized ECG services cardiologists. Any clinical interventions based on these results need to be documented in the appropriate source documents and eCRF as applicable. It is the responsibility of the investigator to obtain additional ECGs required for the clinical management of the subject, using centralized ECG services equipment or equipment on-site.

Further details regarding ECG collection requirements for this study will be provided in an Investigator ECG Manual distributed to the sites before start of enrollment.

